### **8.3.2. Follow-Up of Subjects After Adverse Events**

If an AE/adverse reaction occurs, the Investigator will institute support and/or treatment as deemed appropriate. All SAEs ongoing at the time of the last visit or discontinuation from the study will be followed up until the AE/adverse reaction is resolved or stabilized, the subject is lost to follow-up, or there is other resolution to the event.

## **9. STATISTICS**

### ***9.1. Sample Size***

A sample size of approximately 140 subjects (40 for Nyxol + LDP and Placebo alone arms and 30 for each of the other 2 arms) who are evaluable for efficacy is needed for the study. The primary treatment comparison will be Nyxol + LDP compared to Placebo alone. Using  $\alpha = 0.05$  significance and a two-tailed test, 76 total subjects (38 subjects each in the Nyxol + LDP and Placebo alone arms) evaluable for efficacy will provide at [REDACTED]  
[REDACTED]  
[REDACTED]

Subjects will be randomized 4:3:3:4 to Nyxol + LDP, Nyxol + No Treatment 2 (Nyxol alone), Placebo + LDP, and Placebo + No Treatment 2 (Placebo alone), respectively.

It is assumed that there will be approximately 7% drop-out between Visit 1 and end of Visit 2. To account for this drop-out, a total of approximately 152 subjects will be randomized into the study.

A diagram outlining treatment arms can be found in [Appendix 5](#).

## **9.2. Analysis Populations**

**Modified Intention-to-Treat:** The mITT population will include all randomized subjects who received at least one drop of Treatment 1 and were administered Treatment 2 (LDP or No Treatment). The mITT population will be used to analyze efficacy endpoints.

**Per Protocol Population:** The PP population included all subjects in the mITT who received one drop of Treatment 1 the day prior to Visit 2 and were administered Treatment 2 at Visit 2, had binocular DCNVA and BCDVA in photopic conditions at Baseline (Visit 1) and at Visit 2 time 1 hour, and had no major protocol deviations. The PP population will be used for the primary endpoint analysis and to analyze efficacy endpoints.

**All Randomized Population (ARP):** The ARP will include all randomized subjects. This population is also known as the Intention-to-Treat (ITT) population. The ARP will be used in confirmatory efficacy analyses.

**Safety Population (SP):** The SP will include all randomized subjects who have received at least one drop of study treatment (Treatment 1 or Treatment 2). The SP will be used to summarize safety variables.

## **9.3. Statistical Methods**

### **9.3.1. General Considerations**

All continuous variables will be summarized by treatment and timepoint (as applicable) using descriptive statistics (n, mean, median, standard deviation, minimum, and maximum). All categorical variables will be summarized by treatment and timepoint (as applicable) using frequency counts and percentages.

All study data will be listed by treatment, subject, and timepoint (as applicable).

All statistical tests will be performed using a significance level of 5% (two-tailed). The p-values for the analysis of secondary efficacy endpoints will be considered descriptive.

### **9.3.2. Demographic and Baseline Characteristics**

Demographic and baseline characteristics, such as age, race, and sex, will be summarized by treatment arm using the mITT population, PP population, the ARP, and the SP. These data will also be provided in by-subject listings.

### **9.3.3. Subject Disposition**

Subject disposition, including randomization, and completion and withdrawal from the study will be summarized using the ARP. These data will also be provided in by-subject listings.

### **9.3.4. Medical History and Prior/Concomitant Medications**

Medical history will be coded using the latest version of Medical Dictionary for Regulatory Activities (MedDRA, Version 23.1) and will be summarized by treatment arm using the mITT population.

Prior medications (medications with an end date prior to the date of randomization) and concomitant medications (medications with a start or end date after the date of randomization) will be coded using World Health Organization Drug Dictionary (WHODrug, Sept 2020) and will both be summarized by treatment arm using the SP.

Medical history and prior and concomitant medications will also be provided in by-subject listings.

### 9.3.5. Analysis of Efficacy

Efficacy will be assessed using the mITT and PP populations with subjects included in the treatment arm in which they were randomized. For the analysis of the primary efficacy endpoint, appropriate imputation techniques will be performed for missing observations if applicable; details will be provided in the study Statistical Analysis Plan. The primary comparison of interest is Nyxol + LDP and Placebo alone for the PP population. Confirmatory analyses may be performed using the ARP, with imputation performed for missing data. For the analysis of the secondary efficacy endpoints, only observed case data will be used. If warranted, confirmatory analyses using the ARP with imputation for missing data will also be performed for the secondary efficacy endpoints.

For all efficacy endpoints, Baseline values are defined as the screening assessment values on Visit 1.

All efficacy data will be summarized by treatment group, study day, and timepoint (Baseline and Visit 2), as appropriate.

The primary efficacy endpoint is the percent of subjects with  $\geq 15$  ETDRS letters of improvement in photopic binocular DCNVA on Visit 2 at 1 hour with Nyxol + LDP compared to Placebo alone. The improvement in binocular DCNVA for each subject is relative to the subject's own Baseline value (Visit 1). The primary efficacy endpoint will be analyzed using a logistic regression model with [REDACTED]

The percentage of subjects in each treatment arm meeting the criteria, the odds ratio (OR) with 95% confidence interval (CI) and p-value will be provided. The analysis will be performed using the mITT and PP populations, with subjects included in their randomized treatment regardless of the treatment they actually received. A sensitivity analysis will be completed for the primary efficacy endpoint using the same model but excluding the [REDACTED].

Secondary efficacy endpoints are indicated in [Section 4.1](#).

Each of the continuous secondary efficacy endpoints will be analyzed using analysis of covariance (ANCOVA) with change from Baseline as the dependent variable, treatment, and light/dark irides as factors, and the respective Baseline value included as the covariate. Each ANCOVA will be performed using the mITT and PP populations with subjects included in their randomized treatment regardless of the treatment they actually received. The output from each ANCOVA will include the least-squares mean (LSM) and standard error for all treatment groups, along with the placebo-corrected LSM for each treatment difference, its 95% CI, and associated p-value.

All continuous secondary endpoints derived from VA assessments, such as change in DCNVA, BCIVA, and BCDVA, will be analyzed using ETDRS letters correctly read.

For each of the secondary endpoints related to percent of subjects achieving certain criteria, the analysis will be performed using a logistic regression model with treatment, light/dark irides, and the respective Baseline as a covariate. For each analysis, the percentage of subjects in each treatment arm meeting the criteria, the OR with 95% CI and p-value will be provided. For these endpoints, the mITT and PP populations will be used with subjects included in their randomized treatment regardless of the treatment they actually received.

In addition, each secondary efficacy endpoint will be analyzed by [REDACTED] using the same model indicated above but without irides as a factor, as appropriate. Other subgroups, such as age, sex, and race, may be analyzed as well.

### **9.3.6. Analysis of Safety**

Safety will be assessed using the SP with subjects included in the treatment arm they actually received, regardless of their randomized treatment. Observed case data will be used; no imputation will be performed for missing safety data. A statistical analysis of conjunctival hyperemia will be conducted as described below; otherwise, no statistical analysis of safety data will be performed.

For HR and BP, Baseline is defined as the Screening value. HR and BP values and change from Baseline in the values will be summarized by treatment arm and timepoint (Visit 1 and Visit 2).

Observed values and change from Baseline (Visit 1) in conjunctival hyperemia at each timepoint (Visit 1 at 0 and 1 hour, and Visit 2 at 0 minutes, 30 minutes, 1 hour, 2 hours, 3 hours, 4 hours, and 6 hours), will be summarized for the study eye and fellow eye. Treatments will be compared using the same ANCOVA model proposed for the continuous secondary efficacy endpoints.

For IOP, Baseline is defined as the Screening value. Observed values and change from Baseline in IOP at each timepoint (Visit 1 and Visit 2) will be summarized for the study eye and the fellow eye.

Ocular tolerability values will be summarized by treatment arm at each timepoint (Visit 1 and Visit 2).

Verbatim descriptions of AEs will be coded using MedDRA. Only TEAEs (those that occur after the first dose of study medication *or increasing in severity after initiation of study medication*) will be summarized. TEAEs and SAEs will be summarized by treatment group, by system organ class (SOC), severity, and relationship to study medication. Deaths, withdrawal from study medication due to AEs, and withdrawal from the study due to AEs will each be summarized by treatment group. Note that in MedDRA, ocular events are coded to the SOC of “special senses.” Thus, using SOC in the summaries will provide a separation of ocular and non-ocular AEs.

All safety data will be provided in by-subject listings.

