Regarding safety, Nyxol 1% was well tolerated and there were no major ocular or systemic safety issues. An evening dose regimen minimized eye redness during the daytime while benefiting near VA in an elderly population. The incidence of treatment-emergent adverse events (TEAEs) was higher in the Nyxol arm compared with the placebo arm (31.6% versus 5.0%) but all TEAEs were mild in severity, with no serious TEAEs or TEAEs leading to withdrawal or study medication discontinuation. Most TEAEs were considered related to study medication, with the most frequent being conjunctival hyperemia and burning on instillation (each seen in 16% of subjects treated with Nyxol). Although conjunctival redness scores increased in the Nyxol arm at Day 8, Day 15, and Day 16, the scores in the Nyxol arm at any post-baseline timepoint did not demonstrate a statistically significant difference from scores in the placebo arm. Mean systolic and diastolic BPs and HRs were relatively unchanged and remained within normal range throughout the duration of the trial and were similar between arms. Neither biomicroscopic nor ophthalmoscopic examination showed any clinically significant abnormalities at Screening or at Day 15. There was no worsening of distance VA, near VA, or IOP.

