10.3. Conjunctival Hyperemia

Results from the conjunctival hyperemia assessment, measured with a CCLRU card 4-point scale, will be summarized descriptively using counts and percentages for each treatment group at each time point (baseline, 0 minutes, 30 minutes, 1 hour, 2 hours, 3 hours, 4 hours, and 6 hours) for the observed value and change from baseline. Separate summaries will be created for the study eye and the fellow eye.

Additionally, conjunctival hyperemia will be summarized as a continuous variable. Treatments will be compared using the same ANCOVA model proposed for the continuous secondary efficacy endpoints.

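### The 0-3 hyperemia grade is compared with one pooled-variance ANCOVA across four arms, so the 95% intervals for Nyxol + LDP against a single drug that causes redness could be too narrow

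*Protocol*

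**What the plan says.** Protocol 8.1 lists conjunctival hyperemia among the primary safety measures, on a four-point scale from 0 to 3. Exclusion criterion 14 removes anyone at grade 2 or above, so baseline is 0 or 1.

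Protocol 9.3.6 singles out hyperemia for a statistical comparison: "Treatments will be compared using the same ANCOVA model proposed for the continuous secondary efficacy endpoints". SAP 10.3 first tabulates counts and percentages by grade, then adds: "Additionally, conjunctival hyperemia will be summarized as a continuous variable", and applies the same model.

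The model is described in protocol 9.3.5 and SAP 9.1.2: treatment and light/dark irides as factors, with the baseline value as covariate. On output the protocol says: "The output from each ANCOVA will include the least-squares mean (LSM) and standard error for all treatment groups". SAP 9.1.2 asks for a 95% CI and p-value for Nyxol + LDP against each of the other three arms. Neither document names an unequal-variance, robust or ordinal method. A single pooled residual variance is therefore the natural reading, although it is never stated. The blacked-out example code sits in the primary efficacy and imputation sections, not in SAP 10.3.

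SAP 7.4.1 makes p-values for safety endpoints descriptive.

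**The concern.** On a 0-3 scale that starts at 0 or 1, an arm in which most eyes do not change has a small variance, and an arm in which many eyes redden has a larger one. A difference in mean redness, which is what the analysis looks for, therefore tends to bring a difference in variance.

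Placebo alone supplies 40 of the 140 evaluable subjects. If it varies less than the active arms, it pulls the pooled variance down. That variance is then used for Nyxol + LDP against Nyxol alone and against Placebo + LDP, where Placebo alone plays no part.

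These contrasts show whether adding the second drug adds redness, and the protocol lists the safety of the combination and of each component among its objectives. If the interval is too narrow, a chance difference in either direction is more easily read as real.

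**Working it through.** **Step 1. The plan's own figure.** The protocol states "It is assumed that there will be approximately 7% drop-out between Visit 1 and end of Visit 2". For 140 evaluable subjects, 140 / 0.93 = 150.5, so 151 against about 152 stated: reproduced. The evaluable arms are "40 for Nyxol + LDP and Placebo alone arms and 30 for each of the other 2 arms". For hyperemia itself the documents give no SD, grade distribution or power.

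**Step 2. Inputs.**
- From the documents: arms 40/30/30/40 (combination, Nyxol, LDP, Placebo); two-sided 5%; scale 0-3; baseline 0 or 1; four arms plus irides plus baseline, leaving 140 − 6 = 134 residual df (t = 1.978).
- Anchor from the earlier evening-dosed trial (protocol 2.2): "the most frequent being conjunctival hyperemia and burning on instillation (each seen in 16% of subjects treated with Nyxol", with all TEAEs on placebo at 5.0%. As yes/no outcomes the variances are 0.16 × 0.84 = 0.134 and at most 0.05 × 0.95 = 0.048, nearly threefold apart. This is only a proxy for grade change.
- Assumed: arm SDs, any-rise rates, and 30% of subjects starting at grade 1.

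**Step 3. Formula.** With arm SDs s and sizes n:
- pooled variance MSE = Σ n·s² / 140
- r = √{ MSE·(1/nᵢ + 1/nⱼ) / (sᵢ²/nᵢ + sⱼ²/nⱼ) }
- coverage ≈ 2Φ(1.978·r) − 1, and the interval should be 1/r times as wide as reported.

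*All three active arms at 0.5, Placebo 0.3.* MSE = (100 × 0.25 + 40 × 0.09) / 140 = 0.2043. Against either single drug, r = √(0.2043 / 0.25) = 0.904 and coverage is 92.6%.

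*Redness from LDP only: 0.6 / 0.3 / 0.6 / 0.3.* MSE = (70 × 0.36 + 70 × 0.09) / 140 = 0.225. Against LDP, r = √(0.225 / 0.36) = 0.79 and coverage is 88.2%. Against Nyxol, r² = 0.225 × (1/40 + 1/30) / (0.36/40 + 0.09/30) = 0.01313 / 0.012 = 1.094 and coverage is 96.1%. Against Placebo it is 95.2%.

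| SDs: combination / Nyxol / LDP / Placebo | v Nyxol | v LDP | v Placebo |
|---|---|---|---|
| all equal | 95.2% | 95.2% | 95.2% |
| .5 / .5 / .5 / .4 | 93.9% | 93.9% | 96.1% |
| .5 / .5 / .5 / .1 | 90.8% | 90.8% | 98.0% |
| .7 / .5 / .5 / .3 | 91.8% | 91.8% | 94.5% |
| .6 / .6 / .3 / .3 (Nyxol only) | 88.2% | 96.1% | 95.2% |

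**Step 4. Simulation with graded rises.** 6,000 trials per row, the planned model, one rise in five being two grades.

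| Any rise: combination / Nyxol / LDP / Placebo | v Nyxol | v LDP |
|---|---|---|
| 55 / 16 / 45 / 3% | 93.3% | 88.0% |
| 35 / 16 / 30 / 5% | 93.4% | 89.7% |
| 20 / 16 / 15 / 3% | 91.4% | 91.2% |
| 20 / 16 / 15 / 10% | 93.0% | 93.5% |
| 16 / 16 / 5 / 5% | 89.0% | 95.4% |

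Combination against Placebo stays at about 94-97%. In the first row the half-width against LDP is reported as 0.25 grade where 0.32 is needed. If eyes at baseline grade 1 may improve, the affected contrasts cover about 90-94%.

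**Step 5. Wider grid.** A second simulation (14 scenarios of 20,000 trials, residual SDs from 0.33 to 0.88, improvement allowed) gave 94.9-95.4% with no arm differences. With all three active arms redder than Placebo by a similar amount, it gave 90.9-92.0% against each single drug. With one drug driving redness, it gave 86.7-91.1% against that drug and 95.6-96.0% against the other.

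**Step 6. Timepoint.** At Visit 2, 0 minutes, LDP has not been given. The combination and Nyxol-alone arms have then had the same treatment, as have the two Placebo arms. Any shortfall at that point falls on the contrast with Nyxol alone. Later it depends on what LDP does.

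**Step 7. Remedies.** HC3 standard errors gave 94.1-95.7% in the Step 4 scenarios. Arm-specific variances gave 94.3-95.4% in all 14 scenarios of Step 5. However, if 3% of Placebo subjects rise and none fall, the chance that all 40 are unchanged is 0.97⁴⁰ = 30%, and that arm's variance then cannot be estimated.

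**The case against.** A reader might infer that the intervals against each single drug are in fact too narrow, at roughly 88-93% coverage. The documents do not support that. They give no SDs or grade distribution for any arm, and with equal variances coverage is nominal. If one drug causes most of the redness, only the contrast with that drug is clearly affected.

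The assumed rates are also loosely anchored. The 16% is TEAE incidence over 14 days, not the share of eyes with a higher grade on a morning after an evening dose. Protocol 2.2 reports no significant difference from placebo in redness scores in that trial and says that bedtime dosing limits daytime redness. It gives no redness rate for pilocarpine. Placebo eyes need not be static: in another earlier trial, on a different scale and soon after dosing, placebo redness also rose. All of this stands, and it is why the point is conditional.

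The consequence is also small. Safety p-values are descriptive, SAP 10.3 shows the grade distribution, a two-unit increase is separately an AE, and the primary efficacy result is untouched. This stands too. But descriptive status applies to the p-values; it does not correct the coverage of an interval labelled 95%.

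A reader might also extend the point to the other ANCOVAs that share this model, such as letters read, pupil diameter and IOP. Nothing examined here shows a similar variance pattern for those measures.

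**Conclusion.** The concern holds conditionally. If Placebo alone is less variable than the active arms, the planned intervals for Nyxol + LDP against a redness-causing single drug are too narrow. Under the any-rise rates in Step 4, coverage of the affected contrast or contrasts is about 88-94%; the wider grid reaches 86.7% under stronger assumptions. At 88%, a contrast with no true difference would be flagged about 12% of the time instead of 5%.

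These figures rest on assumed rates and SDs and on reading the ANCOVA as pooled-variance. Which contrast is affected depends on which drug causes redness and on the timepoint. No decision rule depends on the result. It is a modest point, worth correcting because the correction is cheap and does not require knowing the variance pattern in advance.

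**What to change.** In protocol 9.3.6 and SAP 10.3, keep the adjusted mean differences for hyperemia. State that their standard errors, 95% CIs and p-values will use HC3 heteroscedasticity-robust standard errors. Allow arm-specific residual variances only if every arm's variance can be estimated, for the reason in Step 7. Limit the change to hyperemia.

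The cost is one sentence in each document and one program option. Point estimates do not change. Intervals for the affected contrasts widen by roughly 5-30%: 1/0.95 = 1.05 at the mild end, and 0.32/0.25 = 1.28 or 1/0.77 = 1.30 at the severe end (SDs .7 / .3 / .7 / .3).

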### **9.4. Procedure for Accounting for Missing, Unused, or Spurious Data**

For the summarization and analysis of efficacy data, the focus will be on observed case data only. As appropriate, confirmatory efficacy analyses will be performed using imputation for missing data; details of the imputation, if performed, will be included in the study Statistical Analysis Plan. For the summarization of safety data, observed case data only will be used.

### **9.5. Procedure for Reporting Deviations From the Statistical Plan**

Any deviations from the statistical plan will be described and a justification given in the final Clinical Study Report.

## **10. DIRECT ACCESS TO SOURCE DATA AND DOCUMENTS**

The Investigator will permit study-related monitoring visits, audits, IRB review, and regulatory inspection(s) by providing direct access to source data and documents.

## **11. QUALITY CONTROL AND QUALITY ASSURANCE**

The progress of the study will be monitored by onsite, written, and telephone communications between personnel at the Investigator’s site and the Medical Monitor. Should the COVID-19 pandemic restrict monitors from traveling to a site, remote review will be conducted to the extent possible, while still ensuring the study is monitored appropriately per applicable regulations and

guidelines. The Investigator will allow Ocuphire, the Study Monitor, and the Medical Monitor to inspect all eCRFs, subject records (source documents), signed consent forms, records of study medication receipt, storage, preparation, and disposition, and regulatory files related to this study.

## **12. ETHICAL CONSIDERATIONS AND GCP COMPLIANCE**

### ***12.1. GCP Compliance***

The proposed study is subject to all applicable governmental rules and regulations concerning the conduct of clinical trials on human subjects. This includes, but is not necessarily limited to, the approval of IRBs, the Helsinki Declaration, US FDA law, International Council for Harmonisation (ICH) GCP guidelines, obtaining prospective informed consent, monitoring of the conduct of the study and the completeness of the eCRFs by Ocuphire or its designee(s), and appropriate record retention by the Investigator.

### ***12.2. Institutional Review Board***

This protocol, materials used to recruit subjects, and materials used to document consent must be approved by the IRB prior to initiation of the study. Written IRB approval must adequately identify the protocol and informed consent. In addition to approving the protocol, the IRB must also approve the subject information and consent form, as well as any advertising tools that will be used for the study. Copies of all approved materials, all correspondence with the IRB and written approval from the IRB must be made available to Ocuphire, *prior* to the start of subject enrollment into the study.

### ***12.3. Protocol Deviations/Violations***

The Investigator should not deviate from the requirements of this protocol without prior written approval of the Medical Monitor or Sponsor, except in the event of a medical emergency.

A reportable protocol deviation is defined as nonadherence to the protocol that involves inclusion/exclusion criteria, affects subject safety, rights or welfare, or has the potential to affect the integrity of the data. Examples of major protocol deviations include study enrollment by ineligible subject, loss of key data such as equipment malfunction (e.g., pupillometer), and/or use of a prohibited medication during the study.

All protocol deviations will be reported by entering the event in the appropriate eCRF page. Protocol deviations should be reported to the IRB in accordance with IRB-specific guidelines. If there is any question as to whether the deviation is reportable, Ocuphire or designee and the IRB should be contacted.

All changes to the protocol will be made by the Sponsor or designee as an approved amendment to the protocol, submitted to the FDA, and approved by the IRB prior to implementation.

Changes implemented without prior approval will be considered protocol violations.

